7.4. Packaging and Labeling

The label(s) for IP will include Sponsor name, address and telephone number, the protocol number, IP name, dosage form and strength (where applicable), amount of IP per container, lot number, expiry date (where applicable), medication identification/kit number, dosing instructions, storage conditions, and required caution statements and/or regulatory statements as applicable. Additional information may be included on the label as applicable per local regulations.

7.5. Investigational Product Accountability and Disposal

Celgene (or designee) will review with the Investigator and relevant site personnel the process for investigational product return, disposal, and/or destruction including responsibilities for the site versus Celgene (or designee).

7.6. Investigational Product Compliance

The Investigator(s) or designee(s) is responsible for accounting for all study IP that is issued to and returned by the subject during the course of the study. Accurate recording of all study drug administration (including dispensing and dosing) will be made in the appropriate section of the subject's case report form (CRF) and source documents. Study personnel will review the instructions printed on the package with the study subjects prior to dispensing the IP. Investigational product will be dispensed as noted in the Table of Events, [Table 3](#). The subjects will be instructed to return the IP containers, including any unused IP, to the study site at each visit for tablet counts and reconciliation. Subjects will be asked whether they have taken their IP as instructed at each study visit. Any problems with IP compliance will be reviewed with the subject. If a subject misses 4 or more consecutive days of dosing, Celgene must be contacted to

decide whether dosing should resume, or whether the subject should be discontinued from the study, and enter into the Follow-up Period.

Gross compliance problems (eg, missing 4 or more consecutive days of dosing or taking less than 80% of the doses between study visits) should be discussed with Celgene. Compliance will be categorized into 4 classes: < 50%, $\geq 50\%$ to $\leq 80\%$, > 80% to $\leq 120\%$, > 120%.

8. CONCOMITANT MEDICATIONS AND PROCEDURES

Over the course of this study, additional medications may be required to manage aspects of the disease state of the subjects, including side effects from trial treatments or disease progression.

All medications (prescription and non-prescription), treatments, and therapies taken by the subject from screening throughout their entire participation in the study, including those initiated prior to the start of the study, must be recorded on the subject's source document and on the appropriate page of the eCRF. The dose, unit, frequency, route, indication, date the medication was started, and date the medication was stopped (if not ongoing) must be recorded.

8.1. Permitted Concomitant Medications and Procedures

- The following drugs may be used during the trial, but doses must have been stable for 3 months prior to Screening or historical biopsy used for Screening assessment and the subject agrees to maintain stable doses during the course of the study, unless required to adjust doses due to safety reasons: ursodeoxycholic acid, gemfibrozil, metformin, sodium-glucose co-transporter 2 (SGLT2) inhibitors (eg, canagliflozin), dipeptidyl peptidase-4 inhibitors ("gliptins") (such as sitagliptin), glucagon peptide-1 agonists (eg, liraglutide), anti-obesity medications (eg, orlistat, lorcaserin, liraglutide, phentermine-topiramate, or naltrexone-bupropion). If SGLT2 inhibitors, GLP-1 agonists and anti-obesity have been recently discontinued, the treatment must have been stopped for at least 3 months prior to Screening or historical biopsy.
- Thiazolidinediones (eg, pioglitazone) and vitamin E are allowed during the study, but doses must have been stable for 3 months prior to Screening or 3 months prior to historical biopsy used for Screening assessment and the subject agrees to maintain stable doses during the course of the study. If thiazolidinediones (eg, pioglitazone) or vitamin E have been recently discontinued, the treatment must have been stopped for at least 3 months prior to Screening or historical biopsy.

Exceptions may be made to initiation or changing doses of these medications if, in the opinion of the Investigator, a different dose of such medication(s) are needed to support best medical practice in the time frame of study participation AND the new dose will not interfere with subject safety or the interpretation of study results. In such instances, the Sponsor's Medical Monitor and Investigator must concur.

8.2. Prohibited Concomitant Medications and Procedures

The following medications cannot be administered for the specified times prior to the initiation of study IP and for the duration of the study.

- Drugs historically associated with NAFLD (amiodarone, methotrexate, systemic glucocorticoids, tetracyclines, tamoxifen, estrogens at doses greater than those used for hormone replacement, anabolic steroids, valproic acid, and other known hepatotoxins) for the duration of the study
- Vitamin E for treatment of NASH cannot be initiated after Screening.
- Biologic agents (eg, TNF inhibitors), or cytokine inhibitors (eg, tofacitinib) within 3 months of Screening.
- Medications associated with hepatotoxicity risk, such as, but not limited to, acetaminophen > 3 grams/day and niacin > 2 grams/day while on study or within 2 weeks of first study dose.

- Use of an approved agent for treatment of NASH within 6 months prior to Screening or historical biopsy.
- Use of cannabinoid products other than cannabis oils during the study
- Use of live attenuated or investigational SARS-CoV-2 vaccine

Exceptions may be made to use of these medications if, in the opinion of the Investigator, the medication is needed to treat an unrelated medical condition (eg, a brief course of systemic corticosteroids for an asthma exacerbation) AND such medication will not interfere with subject safety or the interpretation of study results. In such instances, the Sponsor's Medical Monitor and Investigator must concur.

8.3. Required Concomitant Medications and Procedures

Other than medications required for local anesthesia related to liver biopsy, there are no required concomitant medications.

Required procedures include liver biopsy.

9. STATISTICAL CONSIDERATIONS

9.1. Overview

This is a Phase 2, multicenter, multinational, double-blind, randomized, placebo-controlled, dose-finding study evaluating the efficacy, safety, PK, [REDACTED] of treatment with CC-90001, compared with placebo, in NASH subjects with either Stage 2, or Stage 3 fibrosis.

The objective of the statistical analysis is to evaluate the efficacy and safety of CC-90001 versus placebo for 52 weeks in subjects with NASH and Stage 2, or Stage 3 fibrosis.

The primary analysis will be performed after all subjects have completed the Placebo-controlled Phase (Weeks 0 to 52). The final analysis will be performed at the study completion, ie, when all subjects have completed the Observational Follow-up Phase. To maintain the blind at the site and subject level, the individual subject treatment assignments will not be revealed to the investigators until after the final database lock following the study completion.

This section outlines the statistical analysis strategy and details will be documented in a separate Statistical Analysis Plan (SAP).

9.2. Study Population Definitions

The Full Analysis Set (FAS) population will consist of all subjects who are randomized and received at least one dose of IP. Subjects will be included in the treatment group to which they are randomized.

The safety population will consist of all subjects who are randomized and received at least one dose of IP. Subjects will be included in the treatment group corresponding to the IP they actually receive.

The per protocol (PP) population will consist of all subjects included in the FAS population who receive at least one dose of IP, have both baseline and post-treatment liver fibrosis score evaluation, and have no important protocol deviations which may affect analyses in the Placebo-controlled Phase. Subjects will be included in the treatment group to which they are randomized.

9.3. Sample Size and Power Considerations

The estimated improvement on ≥ 1 fibrosis score in Stage 3 subjects of 45% for CC-90001 group and 20% for the placebo group is based on a Phase 2 study of selonsertib, which reported a 23% treatment difference (43% in the selonsertib 18 mg group versus 20% in the simtuzumab group-a compound that was not demonstrated to be effective for NASH with a treatment response similar to placebo from other clinical trials) (Loomba, 2018; Neuschwander-Tetri, 2015).

With the above assumed treatment responses for the primary endpoint between the highest CC-90001 dose group and the placebo, and further assuming a similar treatment effect in Stage 2 subjects, the sample size of 60 for the placebo, 200 mg, and 400 mg treatment group and an expected sample size of 10-15 for the 100 mg treatment group provides the ability to determine a dose response with 80% power, and 5% type I error rate.

This sample size was estimated using the multiple comparison and dose-response modeling (MCP-Mod) procedure and considering five dose-response models (linear, log-linear, two Emax shapes and logistic) (Bretz, 2005; R-package “MCPMod”, version 1.0-10.1 August 5, 2017).

Determination of the minimum effective dose (MED) will follow the MCP-Mod method (Bretz, 2005). Based on this method, a dose will be considered as MED if it satisfies the following two criteria: (i) the response rate of the dose is greater than that of placebo by a clinically relevant treatment difference (Δ), and (ii) the lower confidence bound of the response rate of that dose has to be greater than that of placebo. Simulations were run to assess the sensitivity to determine the MED with examples of Δ and 80% confidence intervals of the response rates.

Table 5: Probability of Each Dose to Be Considered the MED for Various Response Scenarios and Delta

Scenarios	Response Rate			MED Probability ^c		
	100 mg	200 mg	400 mg	Dose (mg)	$\Delta=0.10$	$\Delta=0.15$
1 ^b	0.325 (50% of emax ^c)	0.45	0.45	100	52.80%	44.18%
				200	37.06%	39.84%
				400	0.44%	6.30%
				MED not identified	9.70%	9.68%
2	0.2625 (25% of emax)	0.3875 (75% of emax)	0.45	100	30.38%	20.06%
				200	55.86%	49.30%
				400	1.54%	18.62%
				MED not identified	12.22%	12.02%
3	0.25 (20% of emax)	0.325 (50% of emax)	0.45	100	17.48%	8.04%
				200	62.06%	39.30%
				400	4.26%	36.96%
				MED not identified	16.20%	15.70%

Abbreviations: PBO = placebo; MED = minimum effective dose.

Response Rate for PBO=0.2

^b Response rate at the 100 mg dose closer to response rate at the next dose than the other scenarios.

^c emax is the assumed maximum effect of 45%-20%.

^c With assumed sample size being 15 subjects for the 100 mg dose group and 60 subjects otherwise.

Δ clinically relevant treatment difference.

Based upon these assessments, the planned sample size provides high sensitivity to determine a MED when a range of response rates and clinically significant effects are assumed. Details of the simulations and estimations will be further elaborated in the Statistical Analysis Plan. In addition to considering MED purely based on efficacy in response rates, the overall determination of the MED will also account for additional efficacy and safety endpoints.

Therefore, approximately 180 subjects will be randomized in a 1:1:1 ratio to receive CC-90001 (200 mg QD, 400 mg QD) or placebo. Randomization will be stratified by liver fibrosis stage (Stage 2/Stage 3) and by the presence of Type 2 DM (yes/no). Approximately 60 subjects with

Stage 2 or Stage 3 fibrosis will be enrolled per arm. To ensure enrollment of a suitable number of subjects with Stage 3 fibrosis, up to 15 subjects with Stage 2 fibrosis may be enrolled per arm. Randomization to one stratum will be halted once the enrollment target is achieved for that stratum.

Subjects who have been randomized to the 100 mg QD treatment arm prior to implementation of Protocol Amendment 4 will be included in the study populations as appropriate. It is expected that randomization into the 100 mg dose group will be stopped at approximately 10-15 randomized subjects at time of implementation of Protocol Amendment 4. Thus, a total of approximately 195 subjects will participate in the study.

9.4. Background and Demographic Characteristics

Subject's age, height, weight, and baseline characteristics will be summarized using descriptive statistics, while sex, race and other categorical variables will be provided using frequency tabulations. Medical history data will be summarized using frequency tabulations by Medical Dictionary for Drug Regulatory Activities (MedDRA) system organ class and preferred term.

9.5. Subject Disposition

A summary of analysis population allocation will be provided. Subject disposition (entered, discontinued, along with primary reason for discontinuation) will be summarized using frequency and percent for the Placebo-controlled Phase (Weeks 0 to 52) and the Active Treatment Extension Phase (Weeks 52 to 102). A summary of subjects enrolled by site will be provided. Protocol deviations will be summarized using frequency tabulations.

9.6. Efficacy Analysis

9.6.1. Efficacy Evaluation for the Placebo-controlled Phase (Weeks 0 to 52)

For the Placebo-controlled Phase (Weeks 0 to 52), the analyses for efficacy endpoints will be based on the FAS. Statistical comparisons will be made between each of CC-90001 treatment groups versus placebo. All statistical tests will be at the two-sided 0.05 significance level and the corresponding p-values and 95% confidence intervals (CIs) will be reported. No adjustment for multiple comparisons will be made in this phase 2 study. The nominal p-values will be reported to give an indication of the strength of association regarding the treatment differences.

9.6.1.1. Primary Efficacy Endpoint

The primary efficacy endpoint is the proportion of subjects who achieve a ≥ 1 stage improvement in liver fibrosis using the NASH CRN Histological Scoring System at Week 52. It will be analyzed using the FAS.

The estimand of primary interest is defined in terms of the following four attributes:

- A. The population is defined through appropriate inclusion/exclusion criteria to reflect the targeted patient population (FAS);
- B. The variable is the proportion of subjects who achieve a ≥ 1 stage improvement in liver fibrosis at Week 52. Missing values due to early termination will be imputed using data

collected at the early termination visit if available; otherwise missing values will be imputed using the non-responder imputation (NRI) method;

C. Potential intercurrent events are captured through the variable definition (B).

D. The summary measure is the difference in response proportions.

With this missing data handling approach, the estimand answers a clinically relevant question that compares the proportion of subjects who achieve the defined response criteria at Week 52 in the FAS.

The primary efficacy endpoint will be analyzed using the Cochran–Mantel–Haenszel (CMH) test adjusting for the stratification factors (fibrosis stage (Stage 2 /Stage 3) and by the presence of Type 2 DM (yes/no), at randomization) in order to compare each of CC-90001 treatment groups versus placebo. The two-sided p-values from the CMH test, the adjusted treatment difference in proportion using the weighted average of the treatment differences across the strata with the CMH weights, along with the associated two-sided 95% CIs using a normal approximation to the weighted average will be provided. A sensitivity analysis will be performed using the PP population.

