2. STUDY OBJECTIVES AND ENDPOINTS

Table 1: Study Objectives

Primary Objective
The primary objective of the study is to evaluate the effect of oral CC-90001, administered once daily (QD), compared with placebo, on liver histology in subjects with nonalcoholic steatohepatitis (NASH) and Stage 2 or Stage 3 fibrosis.
Secondary Objective(s)
The secondary objectives are: 
• To evaluate the effects of oral CC-90001, administered QD, compared with placebo, in subjects with NASH and Stage 2 or Stage 3 fibrosis, on:
- Additional liver biopsy-based endpoints- Liver biochemistry-based endpoints- Metabolic parameters-based endpoints- Dose response- Safety and tolerability- Pharmacokinetics (PK)

Table 2: Study Endpoints

Endpoint	Name	Description	Timeframe
Primary	Liver fibrosis score	Proportion of subjects who achieve a ≥ 1 stage improvement in liver fibrosis using the nonalcoholic steatohepatitis (NASH) clinical research network (CRN) Histological Scoring System	Week 52
Secondary	Combined assessment of liver fibrosis score and steatohepatitis	Proportion of subjects who achieve a ≥ 1 stage improvement in liver fibrosis and no worsening of steatohepatitis (no worsening of lobular inflammation or hepatocellular ballooning score)	Week 52
	Nonalcoholic fatty liver disease (NAFLD) activity score (NAS)	Proportion of subjects with an improvement of ≥ 2 points in the total NAS in more than one category of steatosis, lobular inflammation, and hepatocellular ballooning, and no worsening of liver fibrosis	Week 52
	Resolution of NASH	Proportion of subjects who demonstrate absence of ballooning, and lobular inflammation score of 0 or 1	Week 52
	Resolution of NASH without worsening of liver fibrosis	Proportion of subjects who demonstrate absence of ballooning, and lobular inflammation score of 0 or 1 and no worsening of liver fibrosis	Week 52
	Progression to cirrhosis	Proportion of subjects who progress to cirrhosis	Week 52
	Liver biochemistry	Change from Baseline in serum aspartate aminotransferase (AST), alanine aminotransferase (ALT) and γ -glutamyl transferase (GGT)	through Week 52
	Metabolic parameters	Change from Baseline in total cholesterol, low density cholesterol (LDL) high density cholesterol (HDL), and triglycerides	through Week 52
	Dose response	Dose-related changes in the primary and secondary endpoints	through Week 24 (secondary endpoints); through Week 52 (primary and secondary endpoints)

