9.6.1.2. Secondary Efficacy Endpoints

The secondary efficacy endpoints will be analyzed based on the FAS. The 2-sided p-values and 2-sided 95% CIs will be reported for treatment difference between each of the CC-90001 treatment groups versus placebo.

The binary endpoints will be summarized using counts and percentages, and the treatment comparison will be performed similarly as the primary endpoint using the CMH test.

The continuous efficacy endpoints will be summarized using mean, standard deviation (SD), median, minimum, maximum, and number of observations analyzed. For all continuous efficacy endpoints, the treatment comparisons will be performed using a mixed model of repeated measures (MMRM) as the primary analysis method of the secondary efficacy endpoints. The MMRM will use the change from baseline as the dependent variable and will include dose, time on treatment, and their interaction as fixed effects covariates. The model will also include the stratification factors (fibrosis stage (Stage 2/ Stage 3) and presence of Type 2 DM (yes/no), at randomization) and corresponding baseline value as fixed effects covariates. Time will be treated as a categorical variable in the MMRM and will be considered as a repeated effect. All post-baseline measurements up to Week 52 will be included in this analysis with no imputation of missing data other than that inherent in the MMRM. Within-group least-squares (LS) means and the associated standard errors (SEs) and 2-sided 95% CIs, treatment differences in LS means and the associated 2-sided 95% CIs and 2-sided p-values will be derived from the MMRM.

As a sensitivity analysis method for all secondary continuous efficacy endpoints an analysis of covariance (ANCOVA) model will be used. The ANCOVA model will use the change from baseline as the dependent variable, treatment group as a fixed factor, and the baseline value and stratification factors (fibrosis stage (Stage 2 /Stage 3) and presence of Type 2 DM (yes/no), at randomization) as covariates. Within-group least-squares (LS) means and the associated standard errors (SEs) and 2-sided 95% CIs, treatment differences in LS means and the associated 2-sided 95% CIs and 2-sided p-values will be derived from the ANCOVA model.

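### The normal-approximation 95% CI planned for every dose covers only about 84-92% for the closed 100 mg arm with either usual variance, and can contradict the CMH p-value beside it

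*Combined protocol and SAP*

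**What the plan says.** Section 9.6.1.1 sets out, for the primary endpoint (improvement of at least one fibrosis stage at Week 52), a CMH test stratified by fibrosis stage and Type 2 diabetes. With it goes a risk difference averaged over strata with CMH weights, "along with the associated two-sided 95% CIs using a normal approximation to the weighted average will be provided". It does not say which variance enters the normal approximation.

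Section 9.6.1 applies this to all doses: "Statistical comparisons will be made between each of CC-90001 treatment groups versus placebo". Section 9.3 expects that "randomization into the 100 mg dose group will be stopped at approximately 10-15 randomized subjects", and that subjects "randomized to the 100 mg QD treatment arm prior to implementation of Protocol Amendment 4 will be included in the study populations as appropriate". Placebo, 200 mg and 400 mg have 60 subjects each.

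For binary secondary endpoints, Section 9.6.1.2 says "the treatment comparison will be performed similarly as the primary endpoint using the CMH test", again with 95% CIs for each dose. One of these endpoints (Section 2, Table 2) is "Proportion of subjects who progress to cirrhosis". Section 9.1 leaves details to a separate SAP, which is not among the documents reviewed.

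**The concern.** A normal approximation for a difference of proportions is unreliable when one arm has 10-15 subjects, and here that arm is also split over four strata. If no responder is seen at 100 mg, the arm contributes nothing to the unpooled variance. The interval then reflects placebo sampling error alone.

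Two things are at stake. The interval reported for 100 mg would not be a 95% interval. It could also exclude zero next to a CMH p-value that is not significant, although Section 9.6.1 offers those p-values as a guide to the strength of association. On the primary endpoint the error mostly makes 100 mg look worse than placebo. On progression to cirrhosis, where fewer events are better, the same error would read as benefit.

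**Working it through.** **The plan's own figures.** The plan states no coverage beyond the nominal 95%. Its stated 80% power for dose response was reproduced: two-sided 5% MCP-Mod power is 83-89% across the candidate shapes (shape parameters assumed). That figure is not in dispute.

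**Inputs from the protocol.** 100 mg n=10-15 and placebo n=60; placebo response 20%; 100 mg response 25%, 26.25% or 32.5% (Section 9.3, Table 5); four strata.

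**Assumptions.** Stage 2 share 25%, which is the 15-per-arm cap over 60. Diabetes share 55%; using 40% or 70% moves coverage by at most 0.3 point. Response rate equal across strata.

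**Formulas.** In stratum i, let n1, n0 be the arm sizes, x1, x0 the responders, p1, p0 the observed rates, N = n1+n0 and m = x1+x0. Then w = n1·n0/N, W = Σw and D = Σw(p1−p0)/W. The interval is D ± 1.96√V, with V one of:

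- Unpooled: Σw²[p1(1−p1)/n1 + p0(1−p0)/n0]/W²
- Sato: (D·ΣP + ΣQ)/W², with P = [n1²x0 − n0²x1 + n1n0(n0−n1)/2]/N² and Q = [x1(n0−x0) + x0(n1−x1)]/(2N)
- Pooled under the null: H/W², with H = Σ n1n0·m(N−m)/[N²(N−1)]

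The CMH statistic without continuity correction is (W·D)²/H.

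**Worked case.** 0/10 on 100 mg against 12/60 on placebo. Strata: 100 mg 1/1/4/4; placebo 8/7/25/20 with 2/1/5/4 responders.

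- w = 0.889, 0.875, 3.448, 3.333, so W = 8.545, W² = 73.03 and D = −0.199.
- Unpooled: V = 0.1969/73.03, SE 0.0519, CI −30.1 to −9.8 points.
- Sato: V = (−0.199×3.280 + 0.852)/73.03, SE 0.0521, CI −30.1 to −9.7 points.
- Pooled-null: V = 1.275/73.03, SE 0.132, CI −45.8 to +6.0 points.
- CMH: 1.7035²/1.275 = 2.28, p=0.13.
- Stratified Miettinen-Nurminen score CI: −32.2 to +9.9 points.

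Both usual variances exclude zero by a wide margin beside p=0.13. At a true 20% response, no responders in 10 has probability 0.8^10 = 10.7% (0.8^15 = 3.5% for n=15).

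**Simulation, 20% in both arms** (100,000 trials per setting):

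| | n=10 | n=12 | n=15 |
|---|---|---|---|
| Coverage, unpooled | 83.6% | 86.6% | 88.6% |
| Coverage, Sato | 87.3% | 89.8% | 91.3% |
| Coverage, pooled-null | 96.2% | 95.8% | 95.4% |
| Coverage, unstratified Wald | 87.6% | 90.1% | 90.6% |
| CI below zero, unpooled / Sato | 12.6 / 11.2% | 10.2 / 8.6% | 8.5 / 7.1% |
| CI above zero, unpooled / Sato | 3.8 / 1.6% | 3.2 / 1.6% | 2.9 / 1.6% |
| CMH rejects | 3.8% | 4.2% | 4.6% |
| CI excludes zero, CMH not significant: unpooled / Sato | 13.1 / 10.5% | 9.8 / 7.5% | 7.3 / 5.6% |

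The unstratified row shows that the small arm is the main cause. Stratification costs a further 2-4 points with the unpooled variance (for example 87.6 − 83.6 = 4.0) and almost nothing with Sato.

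**Table 5 rates (25-32.5% on 100 mg).** Unpooled 85-89%, Sato 90-92%, pooled-null 93-94%.

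**No Stage 2 subjects on 100 mg, n=10/15.** Unpooled 86.3/90.8%, Sato 87.3/91.6%.

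**60 against 60, rates 20-45%.** Unpooled 93.8-93.9%, Sato 94.5-94.6%.

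**Progression to cirrhosis.** The documents give no rate, so 3/5/10/15% in both arms is assumed. False benefit, against a nominal 2.5%:

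| | 3% | 5% | 10% | 15% |
|---|---|---|---|---|
| n=10, unpooled / Sato | 5 / 4% | 16 / 13% | 27 / 24% | 20 / 19% |
| n=15, unpooled / Sato | 6 / 5% | 14 / 12% | 17 / 16% | 10 / 9% |

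The pooled-null and score intervals stay under 1%.

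**The case against.** The strongest reply is that no planned decision uses this interval. Comparisons are nominal and the 100 mg arm is closed. On the minimum effective dose, Section 9.3 says: "Determination of the minimum effective dose (MED) will follow the MCP-Mod method". That is correct, and it limits the consequence to what is reported for 100 mg.

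Second, the variance is unnamed, so the separate SAP could choose the pooled-null form without contradicting Section 9.6.1.1. This also stands, but it means that the text as written admits intervals covering anywhere from about 84% to 96%. Leaving details to the SAP does not undo the normal approximation already fixed in the protocol.

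Third, for Sato the shortfall is not only a matter of width. At a 32.5% response and n=10, its mean width (59.0 points) exceeds the pooled-null width (56.6), yet it covers less (90.0% against 92.7%). Skewness and placement contribute.

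Fourth, the conflict rates above are for no effect. At 25% and 32.5% the Sato figures fall to 5.8% and 2.1% (n=10) and to 2.5% and 0.7% (n=15), and none of these conflicts favours 100 mg. The reverse conflict, a significant CMH test with a Sato interval that includes zero, occurs in 4.9-5.3% of trials at 32.5%. That is further disagreement between the two reported results.

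Fifth, the cirrhosis figures rest on assumed rates and vary sharply with them: Sato coverage at n=10 is 95.5% at a 3% rate and 75.1% at 10%. They show a possible direction of error, not a prediction.

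**Conclusion.** The concern holds. With the unpooled or the Sato variance, the planned 100 mg interval covers about 84-92% on the primary endpoint at the protocol's own arm sizes and response rates. Under no effect it excludes zero beside a non-significant CMH result in roughly 6-13% of trials. Most false exclusions there go against 100 mg; false benefit is 2.9-3.8% (unpooled) or about 1.6% (Sato), against 2.5%. The pooled-null variance is the one normal-approximation version found to escape most of this.

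The primary-endpoint result does not depend materially on the assumed diabetes share, and it persists with no Stage 2 subjects on 100 mg. The secondary-endpoint result depends strongly on an event rate that the documents do not give. The CMH p-values, the 200 mg and 400 mg intervals and the dose-response analysis are not affected.

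**What to change.** In Sections 9.6.1.1 and 9.6.1.2, and in the SAP, replace the normal-approximation interval for 100 mg against placebo with a stratified Miettinen-Nurminen score interval using CMH weights. Its coverage is 95-96% on the primary endpoint and 94-96% at the assumed 3-15% event rates. At a difference of zero its statistic equals the CMH statistic without continuity correction, so interval and test agree; no simulated setting produced a conflict. State that the CMH test is run without that correction.

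For 200 mg and 400 mg the normal approximation can stay, provided its variance estimator is named. Using the score interval for all doses would be tidier in the tables but is not needed for coverage.

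The cost is protocol and SAP wording plus standard software. The 100 mg interval widens: mean width 53 points against 44 (unpooled) or 51 (Sato) at n=10, and 46 against 40 or 44 at n=15. Sample size, CMH p-values and the minimum-effective-dose analysis do not change.
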